6.3.3 Study drug discontinuation and withdrawal of patients from the study

A patient can discontinue study drug and withdraw from the study at any time. If a patient discontinues study drug, a Study Drug Discontinuation visit should be performed before standard of care treatment is initiated, when possible. If the study drug is discontinued on a scheduled visit, the Study Drug Discontinuation visit should be performed instead of the scheduled visit unless the study drug is discontinued at the Week 12 visit.

For patients that discontinue study drug before the Week 2 visit, a Week 2 visit should still be performed according to the original schedule of assessments unless consent is withdrawn. However, if the Study Drug Discontinuation visit is performed within 3 days prior to the Week 2 visit, the scheduled Week 2 visit should be omitted.

For patients who discontinue study drug and are unable to visit the clinic before initiation of standard of care treatment appropriate assessments should be performed to substantiate the reason for study drug discontinuation, e.g. local lab results.

A final follow-up call will be conducted 4 weeks after the last IMP administration according to the assessments described for the Week 16_{TEL} visit.

If a patient discontinues study drug because of an AE, the reason should always be stated as 'adverse event' irrespective of whether the study drug discontinuation was decided by the investigator or due to patient's withdrawal of consent.

Patients who fail to return to the clinic or cannot be reached by telephone for follow-up assessments will be contacted by the study site personnel (2 documented phone calls followed by 1 registered letter) in an attempt to have them comply with the protocol and to document the reason for withdrawal.

Irrespective of when a patient is withdrawn a follow-up call should be conducted 4 weeks after the last IMP dose, according to Week 16_{Tel} (see 6.5.1.8).

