8.3.1 General statistical issues

The comparison of primary interest is between anakinra (2 mg/kg and 4 mg/kg combined) and placebo. The two dose groups of anakinra will be evaluated descriptively.

All statistical tests will be two-sided and performed using a 5 % significance level if not stated otherwise. Results will be presented as the estimated value for each treatment group, anakinra (2 mg/kg and 4 mg/kg combined) and placebo, the estimated difference between groups, the associated two-sided 95 % confidence interval and p-value. The estimated value for each dose group of anakinra and the associated two-sided 95 % confidence interval will

also be presented. For continuous secondary endpoints, if assumption of normal distribution seems to be violated for a specific endpoint, corresponding non-parametric methods will be used to check the robustness of the results.

Continuous variables will be summarized using the number of patients, the mean, the standard deviation, the median, the minimum and the maximum value. Categorical variables will be summarized using frequency counts and percentages.

The laboratory data evaluation will be based on the results from the central laboratory.

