8.3.5 Analysis related to key secondary objective

To evaluate the key secondary objective, the following endpoints will be analyzed:

- Absence of fever during the 24 hours preceding Week 1.

- Change from baseline in physician global assessment of disease activity (VAS) at Week 1.
- Change from baseline in patient/parent global assessment of overall well-being (VAS) at Week 1.
- Change from baseline in CRP at Week 1.

The absence of fever at Week 1 will be analyzed using a logistic regression model with treatment, age at onset of disease (< 16 years, ≥ 16 years) and glucocorticoid use (yes, no) as explanatory variables. Patients who discontinued study drug prior to Week 1 will be treated as having a presence of fever in the analysis. The estimated probability of absence of fever in each treatment group, the estimated odds ratio of anakinra to placebo, the corresponding 95 % confidence interval and the p-value from the model will be presented.

The three continuous endpoints; change in CRP, change in physician's global assessment of disease activity and change in patient/parent global assessment of overall well-being, will be analyzed using a mixed model repeated measurement with the measurements on the individual timepoints (i.e. Baseline and Week 1 or if the Week 1 visit is not performed due to Study drug discontinuation before Week 1 the Study drug Discontinuation visit will be used) as responses and with treatment, age at onset of disease (< 16 years, ≥ 16 years) and glucocorticoid use (yes, no), visit and treatment-visit interaction as fixed effects. For the comparison between anakinra (combined dose groups) and placebo for each endpoint, the estimated difference, the associated 95 % confidence interval and the p-value from the model will be presented.

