8.4.1 Handling of missing data

For the primary endpoint ACR30 the following imputation will be used:

- Patients that discontinue study drug prior to Week 2 will be set to non-responders.
- For patients with missing information in any of the ACR30 components, that specific component will be set to no change. For patients with missing information on fever, the patients will be treated as having a presence of fever.

For the key secondary endpoints the following imputation will be used:

- Patients who have missing information on fever during 24 hours preceding Week 1 will be treated as having a presence of fever in the analysis.
- For the continuous key secondary endpoints repeated measures models will be used to handle missing data.

For the other secondary endpoints no imputation will be performed, i.e., all presentations will be based on observed cases.

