### 8.2 Handling of missing data and outliers

#### 8.2.1 Imputation for efficacy endpoints

For all endpoints related to the primary objective the following imputation will be used:

- Patients that discontinue study drug prior to Week 2 will be set to non-responders.
- For patients with missing information in any of the ACR30 components, that specific component will be set to no change. For patients with missing information on fever, the patients will be treated as having a presence of fever.

For the key secondary endpoints the following imputation will be used:

- Patients who have missing information on fever during 24 hours preceding Week 1 will be treated as having a presence of fever in the analysis.
- For the other secondary endpoints no imputation will be performed, i.e., all presentations will be based on observed data.

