### 12.3 Key secondary efficacy endpoints

The absence of fever at Week 1 will be analyzed in the same way as the primary endpoint using exact statistical methods.

For each of the three continuous endpoints; change at Week 1 in CRP, in physician's global assessment of disease activity and in patient/parent global assessment of overall well-being, descriptive statistics for each treatment group will be calculated. For the comparison between anakinra and placebo, exact rank tests based on Wilcoxon scores will be used. The exact 95% confidence intervals based on the Wilcoxon rank statistic for the Hodges-Lehmann estimate of the treatment difference, will be calculated.

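### For the three continuous key secondary endpoints the SAP no longer says which value represents a patient who stops before Week 1: the discontinuation-visit value can be displaced, and a patient with no Day 2–11 value is omitted

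*SAP*

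**What the plan says.** **Protocol.** Section 8.3.5 says the three endpoints "will be analyzed using a mixed model repeated measurement with the measurements on the individual timepoints" (baseline and Week 1) as responses, and adds that "if the Week 1 visit is not performed due to Study drug discontinuation before Week 1 the Study drug Discontinuation visit will be used". Section 8.4.1 supplies the missing-data method: "For the continuous key secondary endpoints repeated measures models will be used to handle missing data". Non-parametric analysis had a supporting role only; under 8.3.1, if normality looks doubtful, "corresponding non-parametric methods will be used to check the robustness of the results".

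**SAP, analysis.** Section 12.3 makes the rank analysis the only comparison: "For the comparison between anakinra and placebo, exact rank tests based on Wilcoxon scores will be used", with an exact Hodges-Lehmann interval. It does not mention patients who stop before Week 1.

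**SAP, missing data.** Section 8.2.1 has two bullets under its key secondary lead-in. One concerns fever: "Patients who have missing information on fever during 24 hours preceding Week 1 will be treated as having a presence of fever". The other reads "For the other secondary endpoints no imputation will be performed, i.e., all presentations will be based on observed data"; its position suggests that it covers the key secondaries, but its wording does not. The protocol's line on the continuous key secondaries is gone.

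**SAP, windows.** Section 8.1 maps Days 2–11 to Week 1 (nominal Day 8) and Days 12–22 to Week 2 (nominal Day 15). Unscheduled data count, and the value nearest the nominal day is taken, or the earlier one if two are equally near. Nothing requires the patient to be on study drug or not yet on standard of care.

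**Visits after an early stop.** SAP 4.1 and protocol 6.3.3 and 6.5.1.9 ask for a discontinuation visit, before standard of care where possible, and then for the Week 2 visit. Protocol 6.3.3 foresees exceptions: "For patients who discontinue study drug and are unable to visit the clinic before initiation of standard of care treatment", it asks for assessments that support the reason for stopping.

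**Same variables, other form.** In SAP 12.2 the same three variables, dichotomised as ACR components at Week 1, count anyone who stopped before Week 1 as a non-responder.

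**The concern.** When the model was replaced, the accompanying rule on which value represents an early stopper was not restated, and nothing took its place. A two-sample rank test on Week 1 change uses only patients who have a Week 1 value, so handling falls to the visit windows, which were not written for this purpose.

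At stake is the Week 1 treatment difference in a trial where SAP 4.2 expects at least 12 patients at 2:1, about 8 anakinra and 4 placebo. A patient who stops in the first week for lack of efficacy or progression probably has one of the poorest outcomes. Omitting that patient, or using a value improved by other treatment, makes the patient's arm look better than it was. It also leaves the SAP treating the same patient on the same variable as a failure in 12.2 and as absent, or possibly improved, in 12.3.

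**Working it through.** **1. The plan's own figure.** The documents give no effect size, SD, power or stopping rate for these endpoints. The only sizing is 81 patients for the primary endpoint (65% v 25%, 2:1, 90% power). The pooled normal formula gives 23 placebo patients (69 in total). With continuity correction it gives 27 placebo and 54 anakinra, which is 81, so the figure is reproduced. It says nothing about the Week 1 endpoints.

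**2. What happens to a patient who stops before Week 1.**

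| Situation | SAP 8.1 with 12.3 | Protocol 8.3.5 |
|---|---|---|
| Discontinuation visit on Days 2–11 before standard of care, nothing else in the window | Own value used | Own value used |
| Discontinuation visit Day 4, further assessment Day 8 on standard of care | Distances are 4 and 0 days, so the Day 8 value is used | Discontinuation-visit value |
| Only Day 2–11 assessment follows the start of standard of care | That value is used | Also used, if it is the discontinuation visit |
| No assessment on Days 2–11 | Omitted (Week 2, Day 15, lies outside the window) | Discontinuation visit whenever held; otherwise no Week 1 value |

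The first row is the route the documents plan for. The second needs an off-schedule assessment, or a Week 1 visit attended anyway, because no visit is required between an early stop and Week 2.

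**3. Cost of omission at this size.** The smallest two-sided exact Wilcoxon p, without ties, is 2/C(n1+n0, n0):

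- 8 v 4: 2/495 = 0.004
- 8 v 3: 2/165 = 0.012
- 8 v 2: 2/45 = 0.044
- 8 v 1: 2/9 = 0.222
- 7 v 2: 2/36 = 0.056

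Losing three placebo patients, or two placebo and one anakinra, puts p ≤ 0.05 out of reach whatever the data. By inversion, no bounded exact 95% Hodges-Lehmann interval then exists.

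**4. Illustrative power.** All inputs here are assumptions: 8 v 4, normal outcomes, true shift of 1.0, 1.5 or 2.0 SD, and a stop before Week 1 for every patient in either arm whose outcome is worse than a threshold set at the worst 25% or 50% of placebo. There were 4,000 simulated trials per scenario, with the exact test at two-sided 0.05.

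| Handling of stoppers | 25%: 1.0 / 1.5 / 2.0 SD | 50%: 1.0 / 1.5 / 2.0 SD |
|---|---|---|
| Own value before standard of care | 28 / 56 / 80% | 30 / 58 / 80% |
| Worst rank | 27 / 55 / 80% | 25 / 54 / 79% |
| Omitted | 15 / 33 / 57% | 5 / 13 / 26% |
| Value improved by 1 SD | 26 / 54 / 78% | 23 / 49 / 75% |
| Value improved by 2 SD | 16 / 40 / 70% | 8 / 19 / 42% |

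With no true effect the rejection rate stayed at or below 5% under every handling. The patient's own value performs as well as worst rank (within about 4 points). The large losses need omission or a large improvement on other treatment.

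**5. How often the test is reached.** SAP 8.4 tests the key secondaries only after a significant primary result. At 8 v 4, Fisher's exact test reaches 0.05 in favour of anakinra with 7/8 v 0/4, 8/8 v 0/4 or 8/8 v 1/4. At 65% v 25% the probability is 0.1373 × 0.3164 + 0.0319 × (0.3164 + 0.4219) = 0.067, about 7%.

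**The case against.** The strongest reply is that the SAP already delivers the main protection. A discontinuation visit on Days 2–11 becomes the Week 1 value through SAP 8.1, and protocol 6.5.1.9 collects all ACR variables and central laboratory samples at that visit. A reader might infer that the worst early failures are simply dropped or scored on standard of care. The documents do not support this, because the usual early stopper enters with their own value, which costs almost no power.

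A reader might also blame the change of test. That does not hold either. The protocol's model gave no failure score, a patient with only a baseline value contributed no Week 1 value to it, and its discontinuation-visit rule had no condition about standard of care. An exact rank test is a reasonable choice for about 12 patients.

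Protocol 6.3.3 should not be over-read. It asks for evidence of the reason for stopping, such as local laboratory results; it does not make a value on standard of care the Week 1 outcome. A local CRP would not enter, since protocol 8.3.1 bases laboratory evaluation on central results.

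Finally, SAP 8.4 gates these tests and calls all secondary testing exploratory, and SAP 12.4.2 plots individual values, so an odd patient would be visible.

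All of this stands and limits the size of the point. It does not close the gaps: the nearest-to-Day-8 rule can still override the protocol's choice of value, the handling of a patient with no value is not stated, and the contrast with SAP 12.2 is unexplained.

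**Conclusion.** The point holds as a gap in specification. SAP 12.3 and 8.2.1 lost the protocol's rule for early stoppers, and the windows do not fully replace it. A patient with no Day 2–11 assessment is omitted, a later value on standard of care can displace the discontinuation-visit value, and the result conflicts with SAP 12.2.

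The firm part of the size is combinatorial: with 8 anakinra patients, significance becomes impossible once three of four placebo patients are missing. The power figures are conditional. At 25% stopping and a 1.5 SD shift, omission takes power from about 55% to 33%, but only if every stopper lacks a usable value and the assumed effect and threshold hold. The documents give no rates.

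A reader might infer that the difference is necessarily pulled toward zero. That follows only if more placebo than anakinra patients stop early for poor outcome; omitting failures flatters whichever arm has more of them. Because testing is gated and exploratory, the practical consequence lies mainly in the reported estimate and interval. The primary endpoint is unaffected. The matter is worth settling before database lock but does not threaten the trial's main conclusion.

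**What to change.** In SAP 12.3 and 8.2.1:

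1. State that for a patient who stops study drug before Week 1, the discontinuation-visit value is used in preference to any later value, overriding the nearest-to-Day-8 rule in SAP 8.1.
2. State that values obtained after standard of care has started are not used as Week 1 values.
3. Add a sensitivity analysis that gives the worst (tied) rank to patients who stop before Week 1 for lack of efficacy or progressive disease, or who have no usable value, and report the number so scored in each arm.
4. Make clear whether the observed-data bullet in SAP 8.2.1 applies to the continuous key secondaries.

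The cost is a few lines of text and one derivation, fixed before database lock and unblinding. There are two downsides. With several worst-ranked patients the Hodges-Lehmann interval may have an unbounded limit in that analysis. Worst rank for stops unrelated to efficacy is a composite choice that changes what is estimated, which is why it belongs in the sensitivity analysis and not in the main one.

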### 12.4 Other secondary efficacy endpoints

### 12.4.1 Sustained efficacy in ACR-responders

To evaluate sustained efficacy in patients that initially responded to treatment at Week 2 (ACR30, ACR50, ACR70 or ACR90 response criteria), the ACR responses at Week 4, Week 8 and Week 12 will be compared to the response at Week 2. The individual response profiles will be displayed in a Swimmer plot with bars representing the time on study drug and markers for the ACR response achieved at each visit. The purpose is to show onset of ACR response and how it evolves over time in relation to time to treatment discontinuation.

### 12.4.2 Efficacy of anakinra during 12 weeks treatment

The number and percentage of patients with ACR30, ACR50, ACR70 or ACR90 response with absence of fever (during 24 hours before Week 1 or 7 days preceding Week 2, Week 4, Week 8 and Week 12) at Week 1, Week 2, Week 4, Week 8 and Week 12 will be presented in Swimmer plots (ACR response in relation to time on study drug) as mentioned in section 12.4.1.

The number and percentage of patients with absence of fever and absence of rash (during 24 hours before Week 1 or 7 days preceding Week 2, Week 4, Week 8 and Week 12) at Week 1, Week 2, Week 4, Week 8 and Week 12 will be tabulated.

Individual absolute values and percentage change from baseline values over time at Week 1, Week 2, Week 4, Week 8 and Week 12 for CRP, physician's global assessment of disease activity and change in patient/parent global assessment of overall well-being, will be plotted.

The number and percentage of patients with inactive disease at Week 12 will be presented.

Individual absolute values and percentage change from baseline values of JADAS27 at Week 2 and Week 12 will be plotted.

#### 12.4.3 Inactive disease

The number of patients with inactive disease at Week 12 will be presented.

#### 12.4.4 Time to study drug discontinuation

Kaplan Meier curves will be generated for the anakinra and placebo groups of time to study drug discontinuation due to any cause. Patients completing the study without being prematurely discontinued will be censored at Week 12.

Study drug discontinuation due to lack of efficacy or progressive disease will be illustrated in the Swimmer plots specified in section 12.4.1.

### 12.4.5 Glucocorticoid tapering

The number and percentage of patients who have initiated tapering of glucocorticoids at Week 12 will be presented.

For patients that initiated tapering the percentage decrease of glucocorticoid dose at Week 2, Week 4, Week 6, Week 8 and Week 12 compared to baseline will be presented with descriptive statistics. The number of patients that have been able to decrease the glucocorticoid dose with at least 50 % from baseline to Week 12 will be presented.

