8.3.6.4 Glucocorticoid tapering

The number and percentage of patients who have initiated tapering of glucocorticoids at Week 12 will be presented.

The number and percentage of patients that have been able to decrease the glucocorticoid dose with at least 50 % from baseline to Week 12 will be presented.

For patients that initiated tapering the percentage decrease of glucocorticoid dose at Week 12 compared to baseline will be presented by descriptive statistics.

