#### 3.3.4 Other secondary efficacy endpoints

Other secondary efficacy endpoints are:

- Sustained ACR response at Week 4, Week 8 and Week 12 compared to ACR response at Week 2.
- ACR30, ACR50, ACR70 or ACR90 response with absence of fever 24 hours before Week 1 or during the 7 days preceding the visit at Week 2, Week 4, Week 8 and Week
- Absence of rash 24 hours before Week 1 or during the 7 days preceding Week 2, Week 4, Week 8 and Week 12.
- Change from baseline in CRP, Hb, platelet count and ferritin at Week 1, Week 2, Week 4, Week 8 and Week 12.
- Change from baseline in patient/parent global assessment of disease related pain (VAS) at Week 1, Week 2, Week 4, Week 8 and Week 12.
- Inactive disease at Week 12.
- Change from baseline in JADAS27 at Week 2 and Week 12.
- Time to study drug discontinuation for any reason.
- Time to study drug discontinuation due to lack of efficacy or progressive disease.
- Number of patients who have initiated tapering of glucocorticoids at Week 12.
- Number of patients with decreased dose of glucocorticoids by at least 50% at Week 12 compared to baseline.
- Percentage decrease of glucocorticoid dose at Week 12 compared to baseline.
- Efficacy endpoints as described above, of anakinra in the 2 separate dose groups.

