If the investigator judges that a patient must discontinue study drug before the Week 12 visit, a Study Drug Discontinuation visit should be performed before standard of care treatment is initiated, if possible. If the study drug is discontinued on a scheduled visit, the Study Drug Discontinuation visit should be performed instead of the scheduled visit unless the study drug is discontinued at the Week 12 visit. For a patient that discontinues study drug before the Week 2 visit, the Week 2 visit should still be performed according to the original schedule of assessments. However, if the Study Drug Discontinuation visit is performed within 3 days prior to the Week 2 visit, the scheduled Week 2 visit should be omitted. A final follow-up call will be conducted 4 weeks after the last IMP administration according to the assessments described for the Week  $16_{Tel}$  visit in the protocol.

All patients included in the study will be carefully monitored by the investigator and if there is a need, patients can withdraw from the study at any time.

If a patient is on glucocorticoid treatment the dose can be tapered starting earliest at the Week 2 visit. The patient must have reached at least ACR50 response with no fever in the preceding 7 days at the visit initiating tapering.

If a patient develops MAS, the patient will terminate the study drug and will be treated according to standard of care. If the MAS event occurs before the Week 2 visit it is preferred, if possible, that the patient returns to conduct the Week 2 visit according to the schedule of assessments. For all patients that are diagnosed with MAS, irrespective of timepoint in the study, a follow-up call should be conducted 4 weeks after the last IMP administration according to the assessments described for the Week  $16_{\text{Tel}}$  visit before the patient is withdrawn from the study. MAS is defined as an event of special interest in this study and must be reported as an SAE.

Once all patients have conducted the Week 16Tel (End of Study) visit or their last visit in case of early discontinuation, data cleaning activities will be completed and the database will be locked before the final analysis will be conducted.

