# 4.2 Selection of study population

A total of 81 patients was originally planned to be randomized, but fewer patients are expected since recruitment will be stopped earlier. At least 12 patients are expected to be randomized, with a 2:1 allocation (anakinra:placebo).

For inclusion into the study, a patient should have active Still's disease, diagnosed not more than 6 months prior to randomization. Diagnosis of Still's disease:

- a) If < 16 years of age at disease onset, according to adapted ILAR criteria i.e., CARRAcriteria for SJIA.
- b) If  $\geq 16$  years of age at disease onset, according to Yamaguchi criteria.

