# **6** Sample size determination

Assuming the ACR30 response rate with absence of fever at Week 2 is 65 % in patients receiving anakinra and 25 % in placebo patients, 81 evaluable patients (54 anakinra and 27 placebo) would be required to ensure 90 % power in demonstrating that anakinra improves clinical features of Still's disease using a two-sided test at a 5 % significance level. These assumptions are based on the canakinumab and tocilizumab phase 3 clinical studies in SJIA where 65 to 85 % of active patients and 10 to 25 % of placebo patients responded at two weeks,

as well as the Nordstrom study in AOSD where 50 % of anakinra treated patients were in remission after 4 weeks of treatment (Nordstrom et al 2012).

Since recruitment will be stopped before the planned number of evaluable patients have been included, it is anticipated that at least 12 patients will be randomized and included in the analyses.

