# 8 General issues for statistical analysis

The comparison of interest is between anakinra (2 mg/kg and 4 mg/kg combined) and placebo. Due to the small number of patients in the individual dose groups of anakinra, summary tables (except for the drug exposure summary) will not provide results by individual dose groups. Likewise, the randomization was stratified by age at onset of disease (< 16 years,  $\geq$  16 years) and glucocorticoid use (yes, no), but due to the very small number of patients for levels of the stratification factors within each treatment group, descriptive statistics and statistical analyses will generally not be performed by stratification factors. For primary and key secondary efficacy endpoints, dose-level information and stratification allocation will be included in a patient listing.

All statistical tests will be two-sided and performed using a 5 % significance level, if not stated otherwise. Results will be presented as the estimated value for each treatment group, anakinra and placebo, the estimated difference between groups, the associated 95 % two-sided confidence interval and p-value. P-values from statistical analyses will be presented to three decimal places with values below 0.001 displayed as <0.001 and 95 % confidence intervals will be presented to one more decimal place than the raw data.

Continuous data will be summarized using descriptive statistics: n, mean, SD, median, minimum and maximum, unless otherwise indicated. Minimum and maximum will be presented to the same number of decimal places as the raw data and mean, SD, and median will be presented to one more decimal place than the raw data.

Categorical data will be summarized using counts and percentages. Percentages will be suppressed when the count is zero, however the category will still be displayed. The denominator for all percentages will be the number of patients within the treatment group for the population of interest, unless otherwise indicated. Percentages will be presented to one decimal place.

Statistical analyses will be performed using SAS software Version 9.4 (SAS Institute Inc, Cary, North Carolina, United States).

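### The percentage glucocorticoid decrease is summarised only in patients who tapered, and the other two tapering summaries lack a denominator of baseline users

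*SAP*

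**What the plan says.** SAP 3.3.4 lists three glucocorticoid endpoints: how many patients have started tapering, how many have cut the dose by at least half, and "Percentage decrease of glucocorticoid dose at Week 12 compared to baseline". None is limited to a subset.

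SAP 12.4.5 turns these into three summaries:

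- Initiation: "The number and percentage of patients who have initiated tapering of glucocorticoids at Week 12 will be presented". No denominator is given.
- Depth: the sentence begins "For patients that initiated tapering the percentage decrease of glucocorticoid dose", so only taperers enter. Protocol 8.3.6.4 has the same limit: "For patients that initiated tapering the percentage decrease of glucocorticoid dose at Week 12 compared to baseline will be presented by descriptive statistics".
- Reduction by at least half: a number only. Protocol 8.3.6.4 planned a number and a percentage.

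Two other rules decide who is counted. SAP 4.1 sets the condition for tapering: "The patient must have reached at least ACR50 response with no fever in the preceding 7 days at the visit initiating tapering". SAP 8 gives the default denominator: "The denominator for all percentages will be the number of patients within the treatment group for the population of interest, unless otherwise indicated". SAP 7.1 makes the mITT set the population for secondary efficacy endpoints. That set is not limited to glucocorticoid users, and SAP 4.3 shows that both users and non-users are enrolled, because use at inclusion is a yes/no stratification factor.

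**The concern.** A taper may start only after a good clinical response, so the taperers are a group formed after randomization by something the treatment is meant to change. A mean decrease in that group describes how far successful patients came down. It says nothing about baseline users who could not start, and their share may differ between arms. A reader who sees anakinra and placebo columns under the label of the SAP 3.3.4 endpoint may take them as a comparison of randomized groups, which they are not.

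The initiation percentage has the opposite fault. Under the default it includes patients with no dose to taper, and these count as not having tapered. The at-least-half count has no N, and with twice as many patients on anakinra two bare counts cannot be compared by eye.

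At stake is whether the steroid-sparing endpoints can be interpreted by arm. The primary result does not depend on them.

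**Working it through.** The documents give no figure for the tapering rows, so there is nothing to reproduce. The check is who enters each row, followed by the algebra of the denominators. Patient counts below are assumptions: 8 anakinra and 4 placebo, from the at least 12 patients at 2:1 in SAP 4.2, all taken to be in the mITT set. They show how the rows behave. They are not evidence of bias.

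**1. Who enters each row**

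- Endpoint (SAP 3.3.4): no restriction stated.
- Depth (SAP 12.4.5, protocol 8.3.6.4): baseline users who started a taper, hence, if the rule is followed, those who reached ACR50 without fever (SAP 4.1).
- Initiation (SAP 12.4.5 with SAP 8 and 7.1): denominator, by default, all mITT patients in the arm, users and non-users.
- At least half (SAP 12.4.5): numerator only.

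**2. Depth row**

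If non-taperers stay at their baseline dose, then

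mean over all users = (taperers / users) × mean among taperers.

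The taperers-only row drops the first factor. Take the Protocol Appendix 4 example schedule, offered there only as an example for a start dose of 1 mg/kg. The dose prescribed at Week 12 is then zero for a Week 2 start (100% decrease) and 0.25 mg/kg for a Week 8 start (75% decrease). Assume 4 anakinra and 2 placebo users.

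- Case A: 3 of 4 and 1 of 2 taper, all from Week 2. Taperers only: 100 − 100 = 0 points. All users: 3/4 × 100 − 1/2 × 100 = 75 − 50 = +25 points.
- Case B: 2 of 4 taper from Week 2 and 1 of 2 from Week 8. Taperers only: 100 − 75 = +25 points. All users: 2/4 × 100 − 1/2 × 75 = 50 − 37.5 = +12.5 points.

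The restriction hides a difference in A and enlarges one in B, so the direction is open.

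**3. Initiation row**

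percentage of mITT = (users / mITT) × (taperers / users).

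- Equal user shares (4/8 and 2/4), with 3 and 1 starting: 37.5% against 25% of mITT, and 75% against 50% of users. The ratio is 1.5 both ways; only the difference shrinks, from 25 to 12.5 points.
- Unequal shares (6/8 and 2/4), half of users starting in each arm: 3/8 = 37.5% against 1/4 = 25% of mITT, but 3/6 = 50% against 1/2 = 50% of users.
- Unequal shares the other way (3/8 and 4/4), with 2 starting in each arm: 25% against 50% of mITT, but 67% against 50% of users.

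The contrast can move either way, but only if user shares differ between arms. Stratified blocks limit such imbalance. With about 12 patients over four strata, blocks may stay incomplete, so they do not exclude it.

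**4. Can the depth row be empty for placebo?**

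SAP 6 plans on an ACR30 rate without fever that at "Week 2 is 65 % in patients receiving anakinra and 25 % in placebo patients". If 25% is taken as a ceiling for the stricter ACR50 rule, the chance that no placebo user qualifies at Week 2 is at least 0.75 to the power of the number of users: 75%, 56%, 42% or 32% for 1, 2, 3 or 4 users. Starts at Week 4 or Week 8 lower this. An empty or one-patient column is plausible, which is why N matters.

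**5. Is the Week 12 dose known for everyone?**

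Protocol 6.4.6 has medications listed up to the Week 16 telephone contact. For patients who stop study drug, protocol 6.3.3 and 6.5.1.9 place the final call 4 weeks after the last dose. Since 12 − 4 = 8, a patient who stops before about Week 8 may have no recorded Week 12 dose. An all-user summary must show this gap.

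**The case against.** The case for leaving the text alone is substantial.

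- The tapering objective concerns anakinra and placebo patients side by side; it does not use the versus wording of the neighbouring objectives. No difference, interval or test is planned for these rows. This stands, and it keeps the point minor.
- Depth among those who tapered is a legitimate descriptive quantity, openly labelled and already in protocol 8.3.6.4. This stands too. A reader might infer that the SAP departed from the protocol here; it did not. The mismatch is between the endpoint and its summary, and both documents share it.
- Planned output gives part of the context. SAP 8 requires n in every continuous summary, SAP 11 tabulates medication at randomization in the mITT set, and the SAP 12.1 listing shows glucocorticoid use at inclusion. A reader could rebuild an approximate denominator, but not the dose change in users who did not taper.
- The mITT denominator for initiation is an inference from a default. That is so, and one sentence in SAP 12.4.5 would settle it.

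Two stronger readings are tempting. One is that the taperers-only row favours one arm. The documents do not support this: user numbers, start weeks and doses are unknown, and the cases above go both ways. The other is that absence of fever at Weeks 4, 8 and 12 is mis-analysed because SAP 8.5.2 counts only patients without missing fever data. That rule is stated openly and agrees with the observed-data rule in SAP 8.2.1, and fever alone at those weeks is not a listed endpoint in SAP 3.3.4. Counting everyone who stopped as febrile would be a different and debatable estimand, not a correction.

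**Conclusion.** The point holds as a minor reporting improvement. The percentage-decrease row is conditioned on post-randomization response and omits baseline users who did not taper, while the endpoint it reports has no such limit. The initiation percentage, on the default reading, includes patients with nothing to taper, and the at-least-half summary has no N. The first and third statements come directly from the text. The second rests on applying the SAP 8 default to the mITT set.

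The size and direction of any effect on the apparent contrast cannot be derived from the documents; the worked figures depend on assumed counts and on an example taper schedule. The rows are descriptive and untested, and the primary conclusion is unchanged.

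**What to change.** In SAP 12.4.5:

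- State that all three tapering summaries use mITT patients on glucocorticoids at baseline, shown as n/N and % by arm.
- Summarise percentage change in all baseline users with an observed dose, with non-taperers at their actual change (0 if unchanged).
- Show by arm the number with no Week 12 dose because follow-up ended early. Label any version that carries the last recorded dose forward as a supplement, since SAP 8.2.1 allows no imputation for these endpoints.
- Keep the taperers-only row as a labelled supplement.

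For fever at Weeks 4, 8 and 12 (SAP 8.5.2 and 12.4.2), print n/N beside the observed-case percentage and change nothing else.

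The cost is a few sentences and table rows. Glucocorticoid use at inclusion is a stratification factor and medications are already recorded, so no new data and no change to any clinical rule are needed. The limitation is that the all-user summary will be incomplete for patients who stopped study drug early, which the added count makes visible.
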